#### *Sensitivity analysis*

One-way sensitivity analyses will be conducted around key variables, including the most expensive items of resource use, and the frequency of cardiac screening in the usual care arm: i.e. every year versus every 2 years. Sensitivity analysis will be undertaken using an alternative QALY weight obtained from the SF-6D a component of the KDQOL-36™ questionnaire using country-appropriate tariffs. In addition, sensitivity analyses will vary the discount rate from 0-6%.

## 7.7 DATA LINKAGE

To obtain additional data for economic evaluation, we will use data linkage to link Canadian, Australian, and New Zealand participant records to available national / regional / provincial data sets. The period of interest will be from the beginning of the recruitment period to the end of the study period (2016-2020). In Australia, we will apply probabilistic linkage procedures to link data based on patient name, date of birth, sex and postcode. We will link their records to the Admitted Patient Data Collections and the Emergency Department Data Collections for NSW, Victoria and the ACT, and Medicare Australia for outpatient visits, diagnostic tests and medicines prescribed under the Pharmaceutical Benefits Scheme (PBS) for all jurisdictions. In New Zealand, the benefit of a unique National Health Index (NHI) number will allow deterministic record linkage. We will link New Zealand participants to the National Minimum Dataset, National Non-Admitted Patient Collection and the Pharmaceutical Collection. We will capture inpatient encounters, the length of stay and resource utilisation (hospitalisations, procedural costs), physician consultations and emergency services use from these databases. In Canada, unique health care codes will be linked to provincial data to capture resource use of inpatient (CIHI CMG+) and ambulatory care resource use (NACRS), as well as physician claims. Medication use will be captured every 6 months by coordinators from patient interview.

## 8. STUDY POPULATION

### 8.1 RECRUITMENT PROCEDURE

Participants will be recruited through any of the participating centres. Patients will be identified from site kidney transplant waiting lists, and approached when attending routine waiting list review appointments. Patients can also be approached immediately after they are waitlisted for the first time or immediately before activation on the kidney transplant wait list. Study procedure will initiate only once the patients are active on the list.

### 8.2 INCLUSION CRITERIA

- 1) adults aged 18 years of age or older;
- 2) dialysis-dependent and currently being assessed for or active on the kidney transplant waiting list;
- 3) expected to require further screening for CAD prior to transplantation (by current standard of care);
- 4) able to give consent;
- 5) anticipated to undergo transplantation more than 12 months from date of enrolment

### **8.3 EXCLUSION CRITERIA**

- 1) patients with signs or symptoms suggestive of uncontrolled cardiac disease such as unstable coronary syndromes, decompensated heart failure, uncontrolled arrhythmia, and severe valvular heart disease;
- 2) patients on-hold for transplantation due to a medical problem;
- 3) patients with other solid organ transplants;
- 4) multi-organ transplant candidates (e.g. kidney-pancreas transplant candidates);
- 5) patients with planned living donor transplant.

### **8.4 CONSENT**

Informed written consent will be requested using the approved patient information and consent form as per the conduct of Good Clinical Practice. Consent will be sought from participants for linkage of trial records to Medicare data for identification of health system resource use. In an effort to enhance fidelity of the study, permission to contact a treating cardiologist, if present, will be sought.

## **9. PARTICIPANT SAFETY AND WITHDRAWAL**

### **9.1 RISK MANAGEMENT AND SAFETY**

Data will be formally reviewed on a 6 monthly basis by the data safety monitoring board (DSMB) who will receive appropriate data reports. Any recommendations from the DSMB will be communicate directly to the site PI.

### **9.2 HANDLING OF WITHDRAWALS**

Provision for withdrawals and drop outs has been made in determining trial size, therefore replacements will not be required.

## **10. STATISTICAL METHODS**

### **10.1 SAMPLE SIZE ESTIMATION & JUSTIFICATION**

The target total sample size is 3306 patients from 23 sites (7 from Australia, 1 from NZ, 15 from Canada). This number of sites will provide a target number of 1000 patients from Australia, 100 from New Zealand and 2206 from Canada. This equates to recruitment of  $\leq 4$  patients per month per centre. This rate is feasible given current wait-list and transplant volumes from all countries.

### **10.2 POWER CALCULATIONS**

We conservatively estimate an average MACE rate of 6%: MACE rates in the U.S. range from 8.7 % in the first year after a kidney transplant to 13.2 % per year on the waiting list.(41) Unpublished data in Australia and Canada show lower rates of 3% and 8% respectively. The lowest MACE rate would be observed if *all* patients underwent transplantation rapidly (i.e. one year wait-listing (MACE 8%), followed by one year of post transplant follow up (MACE 3%)). In this hypothetical scenario, the

[figure not shown]
average MACE rate would be 5.5%. We estimate that 50% of participants will receive a kidney transplant during the study - therefore the majority of patient follow up time will be accrued on the waiting list (when the MACE rate is high) rather than after a KTX justifying our estimated average MACE rate of 6%.

Using a MACE rate of 6% per year and non-inferiority defined as a Hazard Ratio (HR) of MACE  $< 1.25$ , randomization of **3306 patients** will give us 80% power using a two-sided 5% significance level to claim no screening is non-inferior to regular screening if the absolute difference in MACE in the no screening group is  $< 1.4\%$  higher (i.e. 7.4% versus 6.0 %) than in the regular screening group (Fig 2). This is lower than the 2% absolute increase in MACE Canadian transplant physicians indicated would be unacceptable in a survey prior to our pilot trial.

Enrolment of 3306 patients requires recruitment of  $\leq 4$  patients per month per centre. This rate is feasible, and was achieved in our pilot trial. Figure 2 shows the study power for MACE rates between 5 -13% per year. These calculations take into account the different study follow-up in Canada (5 years) and Australasia (4 years), and allow for a 10% drop-out rate.

Power calculations were performed using the **Non-inferiority Logrank Tests** in PASS 12 (NCSS, LLC. Kaysville, Utah, USA. [www.ncss.com](http://www.ncss.com)).

Figure 2: Study power for MACE rates

- For all power calculations, non-inferiority is defined as an absolute increase in the Hazard Ratio (HR) of MACE  $< 1.25$ , Two-sided alpha is 5%, and the total sample size is fixed at N=3306
- Using a MACE rate of 6% per year and non-inferiority as defined above, randomization of **3306 patients** will give us 80% power using a two-sided 5% significance level to claim no screening is non-inferior to regular screening if the absolute difference in MACE in the no screening group is  $< 1.4\%$  higher (i.e. 7.4% versus 6.0 %) than in the regular screening group.

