## 5. INTRODUCTION/BACKGROUND INFORMATION

### 5.1 LAY SUMMARY

The CARSK trial will enrol people who are already on the kidney transplant waiting list, and who don't have any symptoms of new heart problems. The patients enrolled will stay in the study for a maximum of 4 years in Australia and New Zealand and 5 years in Canada. While they are in the study, people will be followed up as usual – they will not have to have any extra appointments but will receive a 6-monthly phone call to check wait-list status and exclude any CAD events. They will also be asked to complete cost and quality of life questionnaires. The trial will use chance to allocate people to either getting no regular heart testing while they wait for a kidney transplant, or to get regular (every year or every second year) heart testing. We will make sure everyone gets tested if they develop any symptoms of heart problems. The trial will measure what happens to people, and particularly whether they develop any heart problems, whether they get a kidney transplant, and whether they have any heart problems after a transplant. The study is important as we know the most common cause of death for people on dialysis or after a transplant is heart related. We don't know if finding heart disease and trying to treat it early, before it is bothering people, is a good idea – even though this is what is done at the moment. We think testing and treating people who don't have symptoms might cause more problems than it solves - it might remove them from the waiting list unnecessarily, or put them through tests and procedures or operations that they don't really need, and waste a lot of peoples' time and money without good reason. This CARSK study will help us work out whether regular testing is helpful, by showing us whether there is any difference to what happens to people if they are tested or not. The study investigators think it is likely that there will be no difference, so we have used best scientific principles to design the CARSK study to test whether we are right.

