### 10.3 STATISTICAL METHODS TO BE UNDERTAKEN

Efficacy outcomes will be analysed using intention to treat. A significance level of 5% shall be used for all analyses, unless otherwise specified. All analyses will be adjusted for site.

The primary analysis will be an analysis of the time to first occurrence of the primary outcome MACE, using a Cox model with treatment arm as a covariate and stratified by site. This analysis will provide an estimate of the HR, a p-value and CI. Non-inferiority will be claimed if the 95%CI of the HR lies entirely lower than an HR value of 1.25, with the screening arm being the referent group. Superiority will be claimed if the 95%CI lies entirely lower than 1. Proportional hazards assumption will be assessed using log-log survival plots and Schoenfeld residuals.

The outcome of all-cause mortality will also be analyse using a Cox model. The time to all other outcomes will be analysed using a competing risk model, with the competing risk being death. Outcomes which can occur more than once will also be analysed using an Andersen and Gill model (42). This model is a natural extension of the Cox model and unlike the Poisson or Negative Binomial models for count data, does not require the assumption of a constant event rate over time. Robust standard errors using the Sandwich estimator will be applied to ensure the correct p-value and CIs are calculated.

All time to event data will also be graphically summarised using a Kaplan Meier or cumulative incidence curves comparing the two treatment arms.

For all time to event outcomes, a subgroup analysis will conducted to test for a statistical interaction (effect modification) between treatment arm and transplantation. This will be performed by stratifying the survival models by transplant date and testing the HRs between the two strata.

Time off waiting list will be analysed using a negative binomial model, with an offset for total time in study.

Safety outcomes will also be analysed using both intention to treat and per-protocol approaches.

Balance between treatment arms will be assessed by comparing means for continuous variable characteristics, such as age, or by comparing proportion for categorical characteristics, such as sex. If there is any imbalance, then an adjusted analysis for any unbalanced characteristics will be conducted in addition to the analyses stated above, which only account for site.

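### The stated 80% power does not fit together with both the stated recruitment pace and the 2016-2020 study period; a common close gives about 71-75%, full individual follow-up 81-88%

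*Protocol*

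**What the plan says.** Four sections of the Protocol bear on the power.

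- **10.1** gives the size and the sites: "The target total sample size is 3306 patients from 23 sites (7 from Australia, 1 from NZ, 15 from Canada"; and the split: "This number of sites will provide a target number of 1000 patients from Australia, 100 from New Zealand and 2206 from Canada". Both 10.1 and 10.2 put the recruitment rate at no more than 4 patients per month per centre.
- **10.2** sets the assumptions: "Using a MACE rate of 6% per year and non-inferiority defined as a Hazard Ratio (HR) of MACE" below 1.25, with 80% power at a two-sided 5% level. On follow-up and loss it says: "These calculations take into account the different study follow-up in Canada (5 years) and Australasia (4 years), and allow for a 10% drop-out rate".
- **5.1** describes length of stay: "The patients enrolled will stay in the study for a maximum of 4 years in Australia and New Zealand and 5 years in Canada".
- **7.7** gives the only calendar dates, as the period for data linkage: "from the beginning of the recruitment period to the end of the study period (2016-2020").

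Section 10.3 confirms the decision rule: "Non-inferiority will be claimed if the 95%CI of the HR lies entirely lower than an HR value of 1.25".

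The Protocol does not state the accrual period, the minimum follow-up, a closing rule for the primary analysis, an expected or required number of first MACE, or whether the 10% drop-out is cumulative or per year.

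**The concern.** In a time-to-event non-inferiority trial, power depends on the number of events, and the number of events depends on how long people are followed. If the study closes on a common date, a three-year recruitment period leaves the last entrants with only one to two years of observation, and the event count falls well short of what full follow-up would give. The stated pace, the maximum stay in 5.1 and the single study window in 7.7 all point towards such a close. The 80% in 10.2 looks as if it rests on a longer follow-up than those statements allow.

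Power is the justification for 3306 patients. If it is really 71-75%, the chance of failing to show non-inferiority when the two strategies are equivalent is 25-29% instead of 20%.

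**Working it through.** **Inputs from the Protocol.** N = 3306: Canada 2206 at 15 sites, Australasia 1100 at 8 sites. At most 4 patients per month per centre. MACE 6% per year, taken as a hazard of 0.06 or as -ln(0.94) = 0.0619. Margin 1.25, two-sided 5%. Drop-out 10%.

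**Assumptions of mine.** 1:1 allocation, true hazard ratio 1, exponential event times, and uniform accrual with every site open from the first day at the ceiling rate. Drop-out is tried three ways: 10% of patients contribute nothing; 10% are lost evenly over the maximum stay; 10% are lost per year (hazard -ln 0.9 = 0.1054).

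**Step 1: events required for 80% power.**
D = 4(1.960 + 0.842)² / (ln 1.25)² = 630.5, so 631 first MACE.

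**Step 2: accrual time at the ceiling pace.**
Overall 3306/(23×4) = 35.9 months. Canada 2206/(15×4) = 36.8 months. Australasia 1100/(8×4) = 34.4 months.

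**Step 3: reproduce the stated 80%.** With event hazard λ and loss hazard η, the probability of an observed event over time t is λ/(λ+η) × [1 - exp(-(λ+η)t)]. With every participant followed for the full term, λ = 0.06 and 10% loss per year:

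- Canada, t = 5: 0.3629 × (1 - 0.4374) × 2206 = 450
- Australasia, t = 4: 0.3629 × (1 - 0.5161) × 1100 = 193
- Total 643. Power = Φ(ln 1.25 × √643 / 2 - 1.960) = Φ(0.869) = 80.8%

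So the stated figure reproduces under full individual follow-up with annual loss.

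**Step 4: common close at 5 years (Canada) and 4 years (Australasia).** With uniform accrual over A years and close at T, the event probability without loss is 1 - [exp(-λ(T-A)) - exp(-λT)]/(λA). For λ = 0.06:

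- Canada, A = 3.06, T = 5: 0.1867 × 2206 = 412 (mean follow-up 3.5 years)
- Australasia, A = 2.86, T = 4: 0.1417 × 1100 = 156 (mean follow-up 2.6 years)
- Total 568. If 10% contribute nothing, 511 events and power Φ(0.562) = 71.3%

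**Step 5: all readings.** Ranges cover both hazards and, for total loss, both ways of losing 10%.

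| Follow-up rule | Drop-out | First MACE | Power |
|---|---|---|---|
| Full 5/4 years each | 10% per year | 643-661 | 81-82% |
| Full 5/4 years each | 10% total | 726-788 | 85-88% |
| Common close at 5/4 years | 10% total | 511-563 | 71-75% |
| Common close at 5/4 years | 10% per year | 480-494 | 69-70% |
| All close after five calendar years, Australasia capped at 4 | 10% total | 553-607 | 75-78.5% |
| All close after five calendar years, Australasia capped at 4 | 10% per year | 515-529 | 72-73% |

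**Step 6: calendar time for full individual follow-up.** Canada 36.8 months + 5 years = 8.1 years. Australasia 34.4 months + 4 years = 6.9 years. A 2016-2020 window holds at most five.

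**Step 7: what would restore 631 events under the common close at 5/4 years.** With 10% total loss, accrual would have to finish in about 1.4-2.1 years, that is 3306/(23 × 12 × 2.06) = 5.8 to 3306/(23 × 12 × 1.37) = 8.7 patients per month per centre. That is above the stated ceiling of 4.

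**The case against.** The strongest reply is that nothing in the Protocol fixes a common close. The maximum in 5.1 is a lay-summary phrase and can equally mean a cap per participant. Section 10.2 gives 5 and 4 years without calling them a maximum. The schedule in Table 4 has visits out to 60 months. Section 7.6 speaks of a four-year follow-up time. Section 7.7 defines a linkage window for the economic evaluation and is not a closing rule for the primary endpoint. With follow-up counted per participant, recruitment pace costs no events.

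This stands, and it limits the finding. A reader might infer that 80% is unattainable, or that it matches no reading of the follow-up. Neither is supported: full individual follow-up with 10% annual loss gives 81-82%, and with 10% total loss the stated 80% is conservative. Nor do the documents single out one replacement figure, since the two common-close variants give different results.

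It does not remove the conflict. Section 7.7 expressly runs from the start of recruitment to the end of the study, and the reading that rescues 80% overruns that period by about two to three years. It may also be said that accrual inputs and event counts can be left to the statistical analysis plan. That is fair for missing detail, but here the Protocol itself states the power, pace and study period, and they disagree. The text I worked from does not reproduce Figure 2, so any accrual inputs printed there should be checked.

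**Conclusion.** The point holds as a conflict between stated figures. The 80% power, a pace of at most 4 per month per centre and a 2016-2020 study period cannot all be true together. If the pace and period are kept, power is about 71-75% for a common close at 5/4 years with 10% total drop-out (69-70% with annual loss), and about 72-79% if all regions close after five calendar years. If the 80% is kept, follow-up must run per participant and the study lasts about 7-8 years.

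Every common-close variant at this pace that includes the promised drop-out allowance is below 80%. The only one to touch it (631 events, 80.0%) uses the five-calendar-year close, the higher hazard and no drop-out at all.

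The common-close figures are on the favourable side in two respects. The pace is a ceiling: at 3 per month per centre, the close at 5/4 years with 10% total loss gives 433-479 events and 64-69%. And non-cardiovascular death, which 10.2 does not mention, would remove some events under any reading. The results rest on 1:1 allocation, a true hazard ratio of 1 and constant hazards.

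**What to change.** In 10.2, state the accrual period, the closing rule (a common date, or 4/5 years per participant), whether the 10% drop-out is total or annual, and the expected number of first MACE beside the 631 required. Then restate the power that follows:

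- common close at 5/4 years: about 71-75% with 10% total drop-out (69-70% if annual);
- full individual follow-up: 81-88%, with the study period in 7.7 corrected to match.

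Use the same rule in 5.1, 7.7 and 10.2.

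Closing the study when the pooled, arm-blind count reaches 631 first MACE is an option open to the sponsor, not a required correction.

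The cost is a re-run of the calculation and some rewording. No extra patients are needed. Either the stated power becomes less favourable or the stated study period becomes longer.

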### 10.3 STATISTICAL METHODS TO BE UNDERTAKEN

Efficacy outcomes will be analysed using intention to treat. A significance level of 5% shall be used for all analyses, unless otherwise specified. All analyses will be adjusted for site.

The primary analysis will be an analysis of the time to first occurrence of the primary outcome MACE, using a Cox model with treatment arm as a covariate and stratified by site. This analysis will provide an estimate of the HR, a p-value and CI. Non-inferiority will be claimed if the 95%CI of the HR lies entirely lower than an HR value of 1.25, with the screening arm being the referent group. Superiority will be claimed if the 95%CI lies entirely lower than 1. Proportional hazards assumption will be assessed using log-log survival plots and Schoenfeld residuals.

The outcome of all-cause mortality will also be analyse using a Cox model. The time to all other outcomes will be analysed using a competing risk model, with the competing risk being death. Outcomes which can occur more than once will also be analysed using an Andersen and Gill model (42). This model is a natural extension of the Cox model and unlike the Poisson or Negative Binomial models for count data, does not require the assumption of a constant event rate over time. Robust standard errors using the Sandwich estimator will be applied to ensure the correct p-value and CIs are calculated.

All time to event data will also be graphically summarised using a Kaplan Meier or cumulative incidence curves comparing the two treatment arms.

For all time to event outcomes, a subgroup analysis will conducted to test for a statistical interaction (effect modification) between treatment arm and transplantation. This will be performed by stratifying the survival models by transplant date and testing the HRs between the two strata.

Time off waiting list will be analysed using a negative binomial model, with an offset for total time in study.

Safety outcomes will also be analysed using both intention to treat and per-protocol approaches.

Balance between treatment arms will be assessed by comparing means for continuous variable characteristics, such as age, or by comparing proportion for categorical characteristics, such as sex. If there is any imbalance, then an adjusted analysis for any unbalanced characteristics will be conducted in addition to the analyses stated above, which only account for site.

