#### 4.6 STUDY ENDPOINTS

*Primary efficacy endpoint:* major adverse cardiac event (MACE), defined as any of the following: cardiovascular death, myocardial infarction, emergency revascularisation, hospitalisation with unstable angina.

*Primary safety endpoint:* the above MACE endpoint plus complications from cardiac diagnosis or treatment including major bleeding requiring transfusions or hospitalizations, vascular intervention subsequent to cardiac interventions stroke and all-cause death.

*Secondary endpoints:* death, cardiovascular death, procedure-related death, myocardial infarction, emergency revascularisation, stroke, hospitalisation with unstable angina, hospitalisation with heart failure, hospitalisation with arrhythmia, major bleeding, health-related quality of life (QoL), time off list (including number of temporary suspension and duration of each suspension), cost-effectiveness, incidence of permanent removal from list for cardiac causes; incidence of transplantation and cancellation of transplant due to CAD.

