#### 4.7 STUDY ANALYSES

Cox models will be used to assess the time to first MACE event and death. Competing risk models will be used to assess the time to all other outcomes, adjusting for death as the competing risk.

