### 6.2 OUTCOME MEASURES

*Primary efficacy endpoint:* major adverse cardiac event (MACE), defined as any of the following: cardiovascular death, myocardial infarction, emergency revascularisation, hospitalisation for unstable angina.

*Primary safety endpoint:* the above MACE endpoint plus complications from cardiac diagnosis or treatment including major bleeding requiring transfusions or hospitalizations, vascular intervention subsequent to cardiac interventions stroke and all-cause death.

*Secondary endpoints:* death, cardiovascular death, procedure-related death, myocardial infarction, emergency revascularisation, stroke, hospitalisation with unstable angina, hospitalisation with heart failure, hospitalisation with arrhythmia, major bleeding, health-related quality of life (QoL), time off list (including number of temporary suspension and duration of each suspension), cost-effectiveness, incidence of permanent removal from list for cardiac causes; incidence of transplantation and cancellation of transplant due to CAD.

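### The primary safety endpoint counts death from any cause as an event, but the stated model makes death its competing risk

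*Protocol*

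**What the plan says.** **Endpoint.** The synopsis (Protocol 4.6) and Protocol 6.2 define the primary safety endpoint as MACE plus complications of cardiac diagnosis or treatment. The list in 6.2 reads "major bleeding requiring transfusions or hospitalizations, vascular intervention subsequent to cardiac interventions stroke and all-cause death", and 4.6 ends in the same way. The punctuation is loose, but all-cause death is a component on any reading.

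**Model.** Protocol 4.7 states "Cox models will be used to assess the time to first MACE event and death", and then "Competing risk models will be used to assess the time to all other outcomes, adjusting for death as the competing risk". Protocol 10.3 repeats the scheme. MACE is analysed "using a Cox model with treatment arm as a covariate and stratified by site". For mortality, "The outcome of all-cause mortality will also be analyse using a Cox model". For the rest, "The time to all other outcomes will be analysed using a competing risk model, with the competing risk being death".

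**Safety outcomes.** The only sentence in 10.3 specific to safety is "Safety outcomes will also be analysed using both intention to treat and per-protocol approaches". It names analysis approaches, not a model.

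**The concern.** The safety composite is one of the trial's two primary endpoints. A competing event is one that prevents the event of interest from occurring. Where death from any cause is itself an event of interest, no death is left to compete. The protocol nevertheless places this composite, by its residual category, under a model in which death competes.

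At stake is whether deaths count in the safety result. Under the written rule, a participant who dies without an earlier safety event leaves the composite without contributing an event. An arm with more such deaths would not look worse on the composite, and could look better, because those participants can no longer have a non-fatal event. Protocol 5.2 names increased mortality, through procedures or through delayed or refused transplantation, as a possible harm of screening, so deaths are not incidental to this endpoint.

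**Working it through.** The protocol states no figure on this point, so there is none to reproduce. The check compares the endpoint definition with the model assignment.

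**Step 1: which model applies to the safety composite?**

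| Outcome | Model in 4.7 and 10.3 | Role of death |
|---|---|---|
| First MACE | Cox | Cardiovascular death is an event |
| All-cause mortality | Cox | Every death is an event |
| Any other time-to-event outcome | Competing risk model | Death is the competing event |

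The composite contains MACE and all-cause death but is neither of them alone. No sentence exempts it, so it belongs in the third row.

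**Step 2: follow the rule as written.** A death that is the first event is coded as competing. This holds for either common form of the model. A cause-specific model censors the participant at death. A subdistribution model keeps the participant in the risk set without an event. In neither does the death count, so the endpoint in 4.6 and 6.2 is not the one analysed.

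**Step 3: follow the endpoint definition instead.** Every death is now an event and no competing event exists. With F the cumulative incidence of the composite and S its event-free survival, F(t) = 1 − S(t). The subdistribution hazard is −d log(1 − F(t))/dt = −d log S(t)/dt, which is the ordinary hazard. The competing risk model becomes the Cox model. This gives a correct analysis, but only by setting aside the statement that death is the competing risk.

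**Step 4: scale, on assumed rates only.** The protocol gives neither the all-cause death rate *m* nor the non-fatal safety event rate *a*. With constant hazards, the share of first safety events that are deaths is m/(a + m). Rates are per 100 patient-years:

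| | m = 2 | m = 4 | m = 6 |
|---|---|---|---|
| a = 4 | 33% | 50% | 60% |
| a = 6 | 25% | 40% | 50% |
| a = 8 | 20% | 33% | 43% |

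For example, 2/(8 + 2) = 20% and 6/(4 + 6) = 60%. These are not trial estimates. They show only that the share coded out need not be small.

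**Step 5: other outcomes under the same rule.** Cardiovascular death and procedure-related death are deaths by definition. In Table 2, major bleeding includes fatal bleeding (BARC type 5), stroke includes a deficit that leads to death, and the pathological criterion for myocardial infarction can capture a fatal infarction. Coding such a death as the outcome, with other deaths competing, is ordinary practice. The text does not say so. For these outcomes this is a point of wording only.

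**The case against.** The strongest reply is that no sentence names a model for the safety composite. It is caught only by a residual phrase, and an explicit endpoint definition should prevail over a residual phrase. A competent analyst would count deaths as events, the named model would reduce to Cox, and the result would be right. On this view the model is merely unspecified, and such detail can be left to the statistical analysis plan.

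Part of this stands: the sensible reading does lead to the correct analysis, and many analysts would take it. It does not remove the conflict. The residual rule appears in two sections, carries no exception and says that death is the competing risk. An analysis plan could reach the right analysis only by departing from that statement.

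The objection that the consequence is limited also stands. The 1.25 margin and the sample size of 3306 concern MACE, the protocol attaches no margin to the safety composite, cardiovascular deaths count in MACE, and the separate mortality analysis would still show an excess of deaths. The secondary outcomes deserve no more than a clarification.

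**Conclusion.** The concern holds. For one of the two primary endpoints, the written model contradicts the written definition, and both cannot be followed. It should be fixed, but it does not threaten the trial's main conclusion: the MACE analysis and its decision rule, the sample size and the all-cause mortality analysis are untouched.

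No magnitude is claimed, because the protocol gives neither of the rates needed; the 20% to 60% range rests wholly on assumed rates and constant hazards. The conclusion itself needs no numerical assumption. It rests on reading the residual rule in 4.7 and 10.3 as covering every time-to-event outcome not named there, which is what the text says.

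**What to change.** Make two changes, in both 4.7 and 10.3:

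1. State that the primary safety composite is analysed as time to first event with the same Cox model as MACE (treatment arm as covariate, stratified by site), and that death from any cause counts as an event.
2. Reword the general rule: for every other time-to-event outcome, the competing event is a death that does not itself meet that outcome's definition. This covers cardiovascular death, procedure-related death, fatal bleeding, fatal stroke and fatal infarction.

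The second sentence alone would logically resolve the composite as well, since no death would then qualify as competing. Naming the model for a primary endpoint is still worth one sentence.

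The cost is two sentences of text in each section. No new data are needed: death has its own form (CRF12 in the study schedule, section 7.2), and the outcome definitions are already in Table 2. Sample size and follow-up do not change.
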